### Events NOT Meeting the AE Definition

- Unless judged by the Investigator to be more severe than expected for the participant's condition, any clinically significant abnormal laboratory findings, other abnormal safety assessments that are associated with the underlying disease, the disease/disorder being studied within the expectedness for participant's condition, as judged by the Investigator.

- Medical or surgical procedure (e.g., endoscopy, appendectomy): the condition that leads to the procedure is the AE.
- Situations in which an untoward medical occurrence did not occur (social and/or convenience admission to a hospital).
- Anticipated day-to-day fluctuations of preexisting disease(s) or condition(s) present or detected at the start of the study that do not worsen.

## SAE Definition

If an event is not an AE per the definition above, then it cannot be an SAE even if serious conditions are met (e.g., hospitalization for signs/symptoms of the disease under study, death due to progression of disease).

**An SAE is defined as any untoward medical occurrence that, at any dose:**

**a. Results in death.**

**b. Is life-threatening**

The term 'life-threatening' in the definition of 'serious' refers to an event in which the participant was at risk of death at the time of the event. It does not refer to an event which hypothetically might have caused death, if it were more severe.

**c. Requires inpatient hospitalization or prolongation of existing hospitalization**

- In general, hospitalization signifies that the participant has been detained (usually involving at least an overnight stay) at the hospital or emergency ward for observation and/or treatment that would not have been appropriate in the physician's office or outpatient setting. Complications that occur during hospitalization are AEs. If a complication prolongs hospitalization or fulfills any other serious criteria, the event is serious. When in doubt as to whether "hospitalization" occurred or was necessary, the AE will be considered serious.
- Hospitalization for elective treatment of a preexisting condition that did not worsen from baseline is not considered an AE.
- However, all events leading to unplanned hospitalizations or unplanned prolongation of an elective hospitalization must be documented and reported as SAEs.

**d. Results in persistent disability/incapacity**

The term disability means a substantial disruption of a person's ability to conduct normal life functions.

This definition is not intended to include experiences of relatively minor medical significance such as uncomplicated headache, nausea, vomiting, diarrhea, influenza, and accidental trauma (e.g., sprained ankle) which may interfere with or prevent everyday life functions but do not constitute a substantial disruption.

**e. Is a congenital anomaly/birth defect.**

**f. Other situations**

- Medical or scientific judgment will be exercised in deciding whether SAE reporting is appropriate in other situations, such as important medical events that may not be immediately life-threatening or result in death or hospitalization but may jeopardize the participant or may require medical or surgical intervention to prevent one of the other outcomes listed in the above definition. These events are usually considered as serious.
- Examples of such events include invasive or malignant cancers, intensive treatment in an emergency room or at home for allergic bronchospasm, blood dyscrasias or convulsions that do not result in hospitalization, or development of drug dependency or drug abuse.

Any suspected transmission of an infectious agent via a study intervention is also considered an SAE for reporting purposes, as specified below for reporting SAEs.

**Recording and Follow-up of AE and/or SAE**

**AE and SAE Recording**

- When an AE/SAE occurs, it is the responsibility of the Investigator to review all documentation (e.g., hospital progress notes, laboratory reports, and diagnostics reports) related to the event.
- The Investigator will then record all relevant AE/SAE information in the CRF.
- As needed, the Sponsor may ask for copies of certain medical records (e.g., autopsy reports, supplemental lab reports, documents on medical history/concomitant medications, discharge letters), as supporting source documentation. All participant identifiers, except the participant number, will be redacted on these copies before submission to the Sponsor.
- The Investigator will attempt to establish a diagnosis of the event based on signs, symptoms, and/or other clinical information. Whenever possible, the diagnosis (not the individual signs/symptoms) will be documented as the AE/SAE.
- Specific guidance is in the CRF Completion and Monitoring Conventions.

### Assessment of Intensity

The Investigator will assess the intensity of each AE and SAE reported during the study and assign it to 1 of the following categories:

- Mild: A type of adverse event that is usually transient and may require only minimal treatment or therapeutic intervention. The event does not generally interfere with usual activities of daily living.
- Moderate: A type of adverse event that is usually alleviated with additional specific therapeutic intervention. The event interferes with usual activities of daily living, causing discomfort but poses no significant or permanent risk of harm to the research participant.
- Severe: A type of adverse event that interrupts usual activities of daily living, or significantly affects clinical status, or may require intensive therapeutic intervention.

Do not confuse an AE that is assessed as severe with an SAE. Severe is a category used to rate the intensity of an event; both AEs and SAEs can be assessed as severe. An event is defined as “serious” when it meets at least 1 of the predefined criteria specified in the definition of an SAE, NOT when it is rated as severe.

Investigators will reference the NCI-CTCAE, version 5.0 (publication date: 27 November 2017), a descriptive terminology that can be used for AE reporting.

A general grading (severity/intensity; hereafter referred to as severity) scale is provided at the beginning of the above referenced document, and specific event grades are also provided.

If the severity for an AE is not specifically graded by NCI-CTCAE, the Investigator is to use the general NCI-CTCAE definitions of Grade 1 through Grade 5, using his or her best medical judgment.

The 5 general grades are:

- Grade 1 or Mild
- Grade 2 or Moderate
- Grade 3 or Severe
- Grade 4 or Life-threatening
- Grade 5 or Death

Any clinical AE with severity of Grade 4 or 5 must also be reported as an SAE. However, a laboratory abnormality of Grade 4, such as anemia or neutropenia, is considered serious only if the condition meets one of the serious criteria specified below.

If death occurs, the primary cause of death or event leading to death will be recorded and reported as an SAE. “Fatal” will be recorded as the outcome of this specific event and death

will not be recorded as separate event. Only, if no cause of death can be reported (e.g., sudden death, unexplained death), the death per se might then be reported as an SAE.

### Assessment of Causality

- The Investigator will assess the relationship between study intervention and each AE/SAE occurrence:
  - Unrelated: Not reasonably related to the study intervention. AE could not medically (pharmacologically/clinically) be attributed to the study intervention. A reasonable alternative explanation will be available.
  - Related: Reasonably related to the study intervention. AE could medically (pharmacologically/clinically) be attributed to the study intervention.
- A “reasonable possibility” of a relationship conveys that there are facts, evidence, and/or arguments to suggest a causal relationship, rather than a relationship cannot be ruled out.
- The Investigator will use clinical judgment to determine the relationship.
- Alternative causes, such as underlying disease(s), concomitant therapy, and other risk factors, as well as the temporal relationship of the event to study intervention administration will be considered and investigated.
- The Investigator will also consult the IB and/or Product Information, for marketed products, in his/her assessment.
- For each AE/SAE, the Investigator will document in the medical notes that he/she has reviewed the AE/SAE and assessed causality.
- There may be situations when an SAE has occurred, and the Investigator has minimal information to include in the initial report to the Sponsor or its designee. To meet the reporting timeline, the causality assessment is not required for the initial report.
- The Investigator may change his/her causality assessment after considering follow-up information and send an SAE follow-up report with the updated causality assessment.
- The causality assessment is one of the criteria used when determining regulatory reporting requirements.

### Follow-up of AEs and SAEs

- The Investigator will perform or arrange for the conduct of supplemental measurements and/or evaluations, as medically indicated or as requested by the Sponsor to elucidate the nature and/or causality of the AE or SAE, as fully as possible. This may include additional laboratory tests or investigations, histopathological examinations, or consultation with other health care professionals.
- New or updated information will be recorded in the originally completed CRF.
- The Investigator will submit any updated SAE data to the Sponsor within 24 hours of receipt of the information.

### Reporting of SAEs

#### SAE Reporting by an Electronic Data Collection Tool

- The primary mechanism for reporting an SAE in multicenter studies to the Sponsor or its designee will be the electronic data collection tool.
- If the electronic system is unavailable, then the site will use the paper SAE form, specified below, to report the event within 24 hours.
- The site will enter into the electronic system the SAE data within 24 hours after becoming aware of the event. It is expected that the Investigator/Subinvestigator signs off this data in the system and any relevant associated data (e.g., additional laboratory tests, medical records, diagnostic reports, histopathological examinations, or consultation with other health care professionals) will be entered as soon as it becomes available.
- After the study is completed at a site, the electronic data collection tool will be taken off-line to prevent the entry of new data or changes to existing data.
- If a site receives a report of a new SAE from a study participant or receives updated data on a previously reported SAE after the electronic data collection tool has been taken off-line, then the site can report this information on a paper SAE form or to the Sponsor's safety department.
- By exception, an SAE (or follow-up information) may be reported by telephone. The site will complete the electronic SAE data entry immediately thereafter.

#### SAE Reporting by a Paper Form

- SAE reporting on a paper report form may be used in single center studies in addition to the standard electronic CRF and as a back-up method for an EDC system failure. The form includes completion instructions for the Investigator, names, addresses, and telephone and fax numbers. All information from the paper form will be transcribed into the electronic form as soon as the system becomes available.

- Facsimile transmission (fax to mail) of the paper form or any follow-up information is the preferred method for transmission and will be done within 24 hours to the Sponsor or its designee.
- In rare circumstances and in the absence of facsimile equipment, notification by telephone is acceptable with a copy of the form sent by overnight mail or courier service.
- Initial notification via telephone does not replace the need for the Investigator to complete and sign the form within 24 hours after becoming aware of the event.
- Additional documents (e.g., laboratory reports, autopsy report, hospital discharge letter) and relevant pages from the CRF may be required in addition (e.g., medical history, concomitant medication). The data provided will be consistent with the information in the CRF.

### Recording and Reporting of DLTs

- Each event that meets the DLT criteria will be recorded in the CRF within 24 hours after awareness of the event.
- Serious DLTs will be reported in an expedited manner, using the SAE reporting process, as specified above.
- Notification of each DLT related event (nonserious and serious) will be reported to the Sponsor or its designee within 24 hours from the date of awareness.

### Reporting of AESIs

- For a nonserious AESI, the site will complete the specific AESI report form and notify the Sponsor immediately (within 24 hours), using the same process for reporting SAEs, as specified above.
- For a serious AESI, the site will complete an SAE report form, using the SAE reporting process, specified above.

### Reporting of Pregnancies

- Pregnancy will be reported whether related to the study intervention using the applicable paper form.
- The applicable form will be used to report if an abnormal outcome of the pregnancy occurs and the child/fetus sustains an event.
- Facsimile transmission (fax to mail) of the paper form or any follow-up information is the preferred method for transmission and will be done within 24 hours to the Sponsor or its designee.

**Appendix 5 Clinical Laboratory Tests**

The protocol-required clinical laboratory assessments are in the following table:

Laboratory Assessments	Parameters			
Hematology	Red blood cell count Platelet count		Mean corpuscular volume (MCV)	White Blood Cell Count with Differential: 

• Neutrophils

• Lymphocytes

• Monocytes

• Eosinophils

• Basophils

	Hemoglobin Hematocrit		Mean corpuscular hemoglobin (MCH) Mean corpuscular hemoglobin concentration (MCHC)	
Biochemistry	Blood Urea Nitrogen	Potassium	Aspartate aminotransferase	Bilirubin (total) a
	Creatinine	Sodium	Alanine aminotransferase	Protein
	Glucose	Calcium	Alkaline phosphatase	C reactive protein
	Uric acid	Chloride	Gamma Glutamyl Transferase	Lactate dehydrogenase
	Urea	Magnesium	Amylase	Creatine Kinase (CK) b
	Cholesterol	Inorganic phosphate	Lipase	
	Triglycerides			
Routine Urinalysis	
 
• Specific gravity
 
• pH, glucose, protein, blood, ketones, and leukocytes by dipstickc
 
• Microscopic examination (if blood, protein, nitrite, or leukocytes is abnormal).
 
			
Other Screening Tests	
 
• Urine drug screen:
 
• Cocaine, Amphetamine, Methamphetamine, Opiate, Barbiturates, Benzodiazepine, Methadone, Cannabinoids, Tricyclic antidepressants, Cotinine, 3,4-methylenedioxymethamphetamine (Ecstasy)
 
• Ethanol breath test
 
• Hepatitis B surface antigen
 
• Hepatitis B core antibody
 
• Hepatitis C antibody
 
• HIV1/HIV2 antibodies
 
• SARs-CoV-2 according to local requirement
 
• Follicle Stimulating Hormone (to confirm postmenopausal status, female only)
 
• Serum or highly sensitive urine human chorionic gonadotropin pregnancy test to confirm non-pregnant status (females only).
 
• Thyrotropin
 
• Estimated Glomerular Filtration Rate based on Chronic Kidney Disease Epidemiology <small>Collaboration</small> Creatinine Equation (2009)
 
			

CK=creatinine kinase; HIV=human immunodeficiency virus MCH=mean corpuscular hemoglobin; MCHC=mean corpuscular hemoglobin concentration MCV=mean corpuscular volume.

- a In case of increased bilirubin (total), the direct bilirubin will be determined.
- b In case of increased CK, myocardium/brain type (CK-MB) will be determined; if the ratio of CK/CK-MB is above 6, troponin will be determined as well.
- c Only if blood, protein, nitrite, or leukocytes are positive on the dipstick.

CCI

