### 1.3

### Schedule of Activities

Assessments & Procedures	Screening	Admission to CRU					SFU (Televisit)	Notes
Study Day	-28 to -3	-1	1	2	3	4 (EoT)	8 (-1 / +2 days)	
Written informed consent	X							Informed consent to be available before start of any study specific assessments.
Participants resident at CRU		X	X	X	X	X		Admission to CRU in the afternoon on Day -1 until discharge on Day 4 after completion of all study-related activities
Inclusion and exclusion criteria	X	X						Recheck clinical status before administration
Demography	X							Including age (year of birth), sex, race and ethnicity
Full physical examination	X	X				X		
Medical history	X							
Pregnancy test	X	X				X		Pregnancy test using serum (at Screening) and using urine (on Day -1 and End of Study), to confirm non-pregnant status (females only)
Follicle stimulating hormone	X							To confirm postmenopausal status (females only)
Serology	X							HIV, hepatitis B and C SARS-CoV-2
Drug and alcohol screen	X	X						
Clinical laboratory tests a	X	X	X	X		X		After at least 10 hours fasting, Day 1 sampling is predose
Safety 12-Lead ECG	X		X	X		X		Day 1: predose, 1 hour postdose, Day 2 (24 hours postdose), and Day 4 (72 hours postdose) (see Section 8.2.3 for further details)

Assessments & Procedures	Screening	Admission to CRU					SFU (Televisit)	Notes
		-1	1	2	3	4 (EoT)		
Study Day	-28 to -3	-1	1	2	3	4 (EoT)	8 (-1 / +2 days)	
Vital signs	X	X	X	X	X	X		Height and Weight to be collected at Screening only. Day 1: predose, 1, 2, 4, 12 hours; Day 2: 24 hours, Day 3: 48 hours, Day 4: 72 hours
CCI								
Study intervention			X					
AE & SAE review	X	X	X	X	X	X	X	
Concomitant medications review	X	X	X	X	X	X	X	
PK blood sampling (plasma)			X	X	X	X		Day 1: predose, and 0.25, 0.5, 1.0, 1.5, 2, 2.5, 3, 4, 6, 8, and 12 hours postdose; Day 2: 24 and 36 hours postdose; Day 3: 48 hours postdose, Day 4: 72 hours postdose. See Section 8.4 for collection windows and further details. The time and date of each collection to be recorded in eCRF.

aUrine samples will be collected at Screening and times of other clinical labs.

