Prior/Concomitant Therapy	

7. Use of any prescribed medicine or over-the-counter drug (other than occasional use of ibuprofen or paracetamol < 1.5 g/day but including herbal remedies, vitamins, and minerals) within 2 weeks or 5 times the half-life of the respective drug, whichever is longer, before the first dose of study intervention.

8. Use of drugs and herbal remedies with enzyme inducing properties such as traditional Chinese medicine, St. John's Wort, within 3 weeks before the first dose of study intervention; grapefruit or grapefruit juice from 72 hours prior to first dosing

9. Vaccination with an attenuated virus during the last 3 months before the first administration of study intervention.

10. Known hypersensitivity to the study intervention or to one or more of the excipients used

Prior/Concurrent Clinical Study Experience	

11. Use of any investigational drug in any clinical study within 5 half-lives from last administration

Category	Criterion
Diagnostic Assessments	

12. Supine systolic blood pressure > 140 mmHg or < 90 mmHg or diastolic blood pressure > 90 mmHg or < 50 mmHg at Screening or Day 1 prior to dosing (any abnormal blood pressure results may be repeated once and if the repeat result is within the normal range, it is not considered to have met the exclusion criterion).

13. Pulse rate > 90 or < 50 beats per minute at Screening or Day 1 prior to dosing.

14. 12-Lead ECG recording with signs of clinically relevant pathology, in particular QTc according to Fridericia's formula > 450 ms, PR > 210 ms, or QRS duration > 120 ms.

15. ALT and AST, ULN at Screening. Any abnormal value of these parameters may be repeated and if the repeat result is within the laboratory reference range, it is not considered to have met the exclusion criterion.

16. Estimated glomerular filtration rate according to the Chronic Kidney Disease Epidemiology Collaboration Creatinine Equation < 80 mL/min/1.73m^2 at Screening.

17. Screening laboratory values other than AST, ALT for hematology, coagulation, biochemistry, or urinalysis outside the reference range. Minor deviations from normal are allowed if they are not clinically significant.

Category	Criterion

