#### 8.2.4 Clinical Safety Laboratory Tests

- Blood and urine samples will be collected for the clinical laboratory tests listed in [Appendix 5 Clinical Laboratory Tests](#) at the timepoints listed in the SoA. All samples will be clearly identified. The samples for scheduled laboratory tests will be collected in a fasted state. Participants will refrain from food and fluid with the exception of water for at least 10 hours prior to collection. Unscheduled tests may not require a fasted condition.
- Additional tests may be performed at any time during the study, as determined necessary by the Investigator or required by local regulations.
- The tests will be performed by the local laboratories.
- The Sponsor will receive a list of the local laboratory normal ranges before shipment of study intervention(s). Any changes to the ranges during the study will be forwarded to the Sponsor.
- The Investigator will review each laboratory report, document this review, and record any clinically significant changes occurring during the study as an AE, unless it does not meet the AE definition, as specified in [Appendix 4](#). The laboratory reports will be filed with the source documents.
- Additional serum or highly sensitive urine pregnancy tests may be conducted, as determined necessary by the Investigators or required by local regulation, to establish the absence of pregnancy at any time during the study. To confirm postmenopausal status, FSH will be assessed at Screening only.

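### The troponin trigger in Appendix 5 footnote b (CK/CK-MB above 6) runs against its evident purpose: for a given CK, a higher CK-MB switches the requirement off

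*Protocol*

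**What the plan says.** CK is a routine biochemistry parameter in Protocol Appendix 5 and carries footnote b. The footnote has two steps. First: "In case of increased CK, myocardium/brain type (CK-MB) will be determined". Second: "if the ratio of CK/CK-MB is above 6, troponin will be determined as well". It gives no unit, percent sign, assay type or rationale. It is not limited to post-dose samples.

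The Schedule of Activities (Protocol 1.3) places the laboratory panel at Screening, Day -1, Day 1, Day 2 and Day 4, with the note "After at least 10 hours fasting, Day 1 sampling is predose". So only the Day 2 and Day 4 panels follow dosing. ECGs are scheduled on both of those days.

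Protocol 8.2.4 contains the relevant safeguards. On review of results it says: "The Investigator will review each laboratory report, document this review, and record any clinically significant changes occurring during the study as an AE". It also allows the Investigator to order further tests at any point in the study when judged necessary. On who runs the tests it says: "The tests will be performed by the local laboratories".

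CK-MB and troponin are not mentioned anywhere else in the visible text of the protocol or the SAP. Some text is redacted.

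**The concern.** The footnote describes an escalation: total CK is raised, so the fraction that it calls the myocardium/brain type is measured, and that result decides whether troponin follows. The natural reading is that a relatively high CK-MB should lead to troponin. The written ratio does the reverse, because CK-MB sits underneath. The more of the raised CK that CK-MB accounts for, the less the protocol calls for troponin.

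At stake is one step of a safety rule for healthy participants, who gain no benefit from the drug. If the text is followed literally, troponin at a high CK-MB share depends on the Investigator's judgment, at the point where the protocol set out to give a rule.

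**Working it through.** **Inputs.** Trigger: CK/CK-MB above 6 (Appendix 5, footnote b). Panel days: Protocol 1.3. Participants: 24 planned, at most 32 (Protocol 9.2). The documents give neither the rate of raised CK nor any CK-MB values, so the CK and CK-MB levels below are illustrative.

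**Direction.** For fixed CK, CK/CK-MB falls as CK-MB rises. Raising CK-MB can therefore only turn the trigger off. This holds for any positive cut-off and for any units.

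**Switch point in a common unit (assumption).** CK/CK-MB > 6 is the same as CK-MB/CK < 1/6 = 16.7%. The switch point is CK-MB = CK/6:
- CK 300: 300/6 = 50
- CK 500: 500/6 = 83.3
- CK 1000: 1000/6 = 166.7

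Troponin is required below these values and not required at or above them. If CK-MB were reported in ng/mL and CK in U/L, the switch point at CK 1000 would be 166.7 ng/mL. The direction would be the same, but the 16.7% share would not apply.

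**Written rule against two possible intentions, at CK 1000, same unit.** Neither intended cut-off is in the documents. Reading A is CK-MB above 6% of CK. Reading B keeps the cut-off and reverses the inequality (share above 1/6). The last column swaps numerator and denominator and keeps the plain number 6.

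| CK-MB | Share | CK/CK-MB | Written | A: > 6% | B: > 1/6 | CK-MB/CK > 6 |
|---|---|---|---|---|---|---|
| 40 | 4% | 25 | yes | no | no | no |
| 100 | 10% | 10 | yes | yes | no | no |
| 160 | 16% | 6.25 | yes | yes | no | no |
| 170 | 17% | 5.88 | no | yes | yes | no |
| 250 | 25% | 4 | no | yes | yes | no |

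Against A, the written rule adds tests at shares of 6% or less, agrees between 6% and 16.7%, and omits troponin from 16.7% upward. Against B it is the opposite, apart from the boundary. Under both readings the omission is confined to high shares. The last column never triggers, because CK-MB/CK in one unit cannot exceed 1.

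**Reach.** There are five scheduled panels, three before dosing and two after.
- 24 participants: 5 × 24 = 120 panels, of which 3 × 24 = 72 are before and 2 × 24 = 48 after dosing.
- 32 participants: 5 × 32 = 160 panels, of which 3 × 32 = 96 are before and 2 × 32 = 64 after dosing.

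Panels of screen failures are not counted. For drug safety the relevant ceiling is 48 or 64. Only panels with raised CK and a high CK-MB share are affected; that number is unknown and may be zero.

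**The case against.** The strongest reply is that the wrong direction is inferred. The footnote states no purpose, and only its sequence and the word myocardium show what was meant. That is fair as to certainty. But no visible text offers a reason to require troponin at a low CK-MB share and drop the requirement at a high one, so the inference stands. The intended cut-off remains unknown.

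The second reply concerns weight, and most of it stands. CK-MB is itself a required test and its result must be reviewed. Protocol 8.2.4 lets the Investigator add tests at any time, without first declaring an adverse event. Appendix 4 further obliges the Investigator to arrange medically indicated work-up of adverse events. Below 16.7% the written rule still requires troponin.

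A reader might go further in three ways that the documents do not support:
- **That a cardiac event would be missed.** The footnote does not forbid troponin at a high share, and the safeguards above remain, including ECGs at 24 and 72 hours.
- **That all 120 or 160 panels are exposed.** Of these, 72 or 96 precede dosing. Eligibility review also applies before dosing, although exclusion criterion 17 does not rule out a raised CK at Screening: "Minor deviations from normal are allowed if they are not clinically significant".
- **That a laboratory is already running a reversed automatic order.** No such order is described. Protocol 8.2.4 assigns testing to local laboratories, while SAP 15.3 refers to a central laboratory.

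**Conclusion.** The point holds as a minor one. The direction of the written rule is arithmetic and does not depend on units. That this direction is wrong is a sound inference from the footnote's own sequence. The 16.7% switch point assumes that CK and CK-MB share a unit. The consequence is limited to the second step of the rule at high CK-MB shares, within at most 48 or 64 scheduled post-dose panels and possibly in none of them. The PK endpoints and the sample size are unaffected.

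**What to change.** Reword footnote b along these lines: *If CK is raised, measure CK-MB; if CK-MB is more than 6% of total CK (both in the same unit), also measure troponin.* The sponsor and the testing laboratory should confirm the cut-off and the unit for the assay in use.

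The 6% assumes that the written 6 was meant as a percentage. It is a safe default, because any share above 1/6 is also above 6%, so it catches every case that simply reversing the inequality would catch. Merely swapping numerator and denominator is not enough, since that version would never trigger.

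The cost is one footnote and possibly a few more troponin tests than a 1/6 cut-off would require, at shares above 6% and up to 16.7%. No visit, scheduled sample or PK analysis changes.
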